3.2 Primary Endpoint

The primary endpoint of efficacy is to determine the percentage of subjects with a serum testosterone concentration suppressed to castrate levels (≤ 50 ng/dL) on Day 28 ± 1 day (week 4) following the first injection of LMIS 25 mg, and the proportion of subjects with serum testosterone suppression (≤ 50 ng/dL) from Day 28 ± 1 day (week 4) through Day 168 ± 5 days (week 24) until the end of the study.

3.3 Secondary Endpoint

Efficacy:

- The mean acute-on-chronic (surge) changes in testosterone and LH levels from just prior to the second injection through 14 days after the second injection of LMIS 25 mg (Days 85-87, week 13; Day 98 [14 days post the second dose], week 14)
- Effect of LMIS 25 mg on change of serum prostate-specific antigen (PSA) levels
- Effect of LMIS 25 mg on change of serum LH levels
- The percentage of subject with PSA relapse defined as after achieving the serum PSA level ≤ 4 ng/mL post LMIS 25 mg injection but with an increase in serum PSA of $>50\%$ PSA nadir by Day 168 (week 24)
- The percentage of subject achieving normal serum PSA level (<4 ng/mL) on Day 168 ± 5 days (week 24)
- The percentage of subjects with enhanced serum testosterone concentration suppression to ≤ 20 ng/dL on Day 28 ± 1 day (week 4) and on Day 168 ± 5 days (week 24)

Safety:

- Adverse event (AE)/ serious adverse event (SAE) reporting
- Assessment of injection site reaction
- Change in bone pain measurement (by Visual Analogue Scale [VAS] scale)
- Change in urinary signs and symptoms and total scores (by the International Prostate Symptom Score, I-PSS sheet)
- Change in vital signs (BP, HR, RR, weight)
- Change in physical examinations with clinical significance compared to baseline by principal investigator's judgment

Statistical Analysis Plan

- Change in lab data, including liver function (AST, ALT, ALP), renal function (BUN, SCr), complete blood count with platelets, clinical chemistries (K, Na, Mg, Ca and P), urinalysis, serum glucose, lipid profile (LDL, HDL, triglycerides), and HbA1c level
- Clinically significant changes in 12-lead resting electrocardiogram (ECG) per the investigator's judgment
- Change from baseline in the ECG parameters of QTcF, HR, PR, and QRS
- Change from baseline in the ECG parameters of QTcF, HR, PR, and QRS in relation to the serum concentrations of leuprolide and testosterone

3.4 Study Population

Inclusion Criteria

Subjects must meet all of the following inclusion criteria to be eligible for enrollment into the study:

1. Males aged ≥ 18 years old
2. Males with histologically confirmed cancer of the prostate
3. Subjects who are judged by the attending physician and/or principal investigator to be a candidate for androgen ablation therapy
4. Baseline morning serum testosterone level > 150 ng/dL performed at screening visit
5. Eastern Cooperative Oncology Group (ECOG) Performance score ≤ 2
6. Life expectancy of at least 18 months
7. Laboratory values
 - Absolute neutrophil count $\geq 1,500$ cells/ μ L
 - Platelets $\geq 100,000$ cells/ μ L
 - Hemoglobin ≥ 10 gm/dL
 - Total bilirubin $\leq 1.5 \times$ upper limit of normal (ULN)
 - AST (SGOT) $\leq 2.5 \times$ ULN
 - ALT (SGPT) $\leq 2.5 \times$ ULN
 - Serum creatinine ≤ 1.5 mg/dL
 - Lipid profile within acceptable range according to investigator's opinion

- Serum glucose within acceptable range according to investigator's opinion
 - HbA1c $\leq 9.5\%$
 - Clinical chemistries (K, Na, Mg, Ca and P) within acceptable range according to investigator's opinion
 - Normal urinalysis results within:
 - ✓ RBCs ≤ 3 RBCs/hpf
 - ✓ WBCs ≤ 5 WBCs/hpf
 - ✓ Nitrate: negative
 - ✓ Glucose: <0.1 g/dL; but <1.0 g/dL in subjects with diabetes mellitus
8. Agree to use male contraceptive methods during study trial
 9. In the investigator's opinion, the ability to understand the nature of the study and any hazards of participation, and to communicate satisfactorily with the investigator and to participate in, and to comply with, the requirements of the entire protocol
 10. All aspects of the protocol explained and written informed consent obtained

Exclusion Criteria

Subjects presenting with any of the following will not be included in the present study.

1. Receipt of chemotherapy, immunotherapy, cryotherapy, radiotherapy, or anti-androgen therapy concomitantly, or within 8 weeks prior to screening visit, for treatment of Cancer of the prostate. Radiation for pain control will be allowed during the study.
2. Receipt of any vaccination (including influenza) within 4 weeks of screening visit
3. History of blood donation within 2 months of screening visit
4. History of anaphylaxis to any LH-RH analogues
5. Receipt of any LH-RH suppressive therapy within 6 months of screening visit
6. Patients who were previously enrolled in the LMIS 50 mg study
7. Major surgery, including any prostatic surgery, within 4 weeks of screening visit
8. History and concomitant clinical and radiographic evidence of central nervous system/spinal cord metastases and subjects at risk for spinal cord compression
9. Clinical evidence of active urinary tract obstruction and subjects at risk for urinary obstruction

10. History of bilateral orchiectomy, adrenalectomy, or hypophysectomy
11. History or presence of hypogonadism, or receipt of exogenous testosterone supplementation within 6 months of screening visit
12. Clinically significant abnormal ECG and/or history of clinically significant cardiovascular disease as judged by the investigator
13. History of drug and/or alcohol abuse within 6 months of screening visit
14. Contraindication to leuprolide or an LH-RH agonist as indicated on package labeling
15. Use of 5-alpha reductase inhibitor within the last 6 months of screening visit
16. History or presence of insulin-dependent diabetes mellitus (Type I). Presence of well controlled diabetes mellitus Type II will be allowed if only oral hypoglycemic are required. Prostate cancer subjects with poor controlled diabetes mellitus with Hb1Ac > 9.5% or urine glycosuria > 1.0 g/dL should be excluded.
17. Use of systemic corticosteroids at a dose > 10 mg/d or anti-androgens
18. Use of any investigational agent within 4 weeks of screening visit
19. Use of any over-the-counter (OTC) medication within 4 weeks of screening visit except for those listed in the permitted Concomitant Treatment section.
20. Uncontrolled intercurrent illness that would jeopardize the subject's safety, interfere with the objectives of the protocol, or limit the subject's compliance with study requirements, as determined by the investigator in consultation with the sponsor

4. GENERAL STATISTICAL ISSUES

For data listings, all raw data will be displayed exactly as provided. Partial date(s) will be listed as provided in the listings. The partial date(s) will be imputed when using for calculation. For the start date, a missing month is supplied a default value of January and a missing day is supplied a default value of 1. For the stop date, a missing month is supplied a default value of December and a missing day is supplied a default value of the last day of the month. The Baseline is defined as the last observation prior to first dose unless otherwise specified.

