11. SAFETY ANALYSIS

11.1 Adverse Events

All AEs will be coded by system organ class and preferred term for analysis. Treatment-emergent adverse event (TEAE) is defined as AEs occur after the first administration of study drug, or AEs occur before the first administration of study drug and worsen in severity after first dose. Unless otherwise specified, all adverse event summaries will include the TEAEs only. For purposes of the summary tables, AEs will be classified as either related or not related to study drug. The drug-related AEs are assessed as 'Definite', or 'Possible' related to study treatment. If the relationship is missing, the AE will also be assessed as drug-related AE. This summary will present the number and percentage of subjects, as well as number of events. For subject with the same AE but multiple different severity/relationship (which resolution date=onset date or resolution date=onset date+1, except they have different AE No), the multiple event will be combined as one AE with the maximum severity/ relationship category for analysis.

A general summary includes number of events, number and percentage of subjects reporting adverse events of all TEAEs will be provided in Table 14.3.1.1.1 according to the following categories:

- Subject with any TEAE
- Subject with any drug-related TEAE

Also, a general summary of all TEAEs will be provided in Table 14.3.1.1.2 according to the following categories:

- TEAEs by severity
- TEAEs by relationship
- Serious TEAEs

- Drug-related TEAEs by severity

Other summary tables for adverse events will be summarized by MedDRA system organ class and preferred term include:

Table 14.3.1.2: Treatment-Emergent Adverse Events - MedDRA

Table 14.3.1.3: Treatment-Emergent Adverse Events by Severity - MedDRA

Table 14.3.1.4: Treatment-Emergent Adverse Events by Relationship to Study Drug - MedDRA

Table 14.3.1.5: Treatment-Emergent Adverse Events for Grade ≥ 3 – MedDRA

Table 14.3.1.6: Drug-Related Treatment-Emergent Adverse Events by Severity – MedDRA

Table 14.3.1.9: Treatment-Emergent Adverse Events - MedDRA (Preferred Term over XX %)

The listing of all AEs will be provided in Listing 16.2.7.1. In addition, TEAEs leading to study discontinuation will be provided in Listing 16.2.7.2.

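### Partial adverse event start dates default to 1 January or the 1st of the month with no check against first dose, so post-dose events can drop out of every TEAE table

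*SAP*

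**What the plan says.** SAP section 4 gives one general rule for incomplete dates. Listings show the date as recorded, but "The partial date(s) will be imputed when using for calculation". The start-date rule is "a missing month is supplied a default value of January and a missing day is supplied a default value of 1". Stop dates go to the other extreme: "For the stop date, a missing month is supplied a default value of December", with a missing day set to the last of the month. Neither rule refers to the date of first dose.

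SAP 11.1 has two routes to treatment emergence. The first is "Treatment-emergent adverse event (TEAE) is defined as AEs occur after the first administration of study drug". The second is "AEs occur before the first administration of study drug and worsen in severity after first dose". It then sets the scope of the tables: "Unless otherwise specified, all adverse event summaries will include the TEAEs only".

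No rule specific to adverse event dates appears in SAP 11.1, in SAP 5.2 (missing data), or in protocol 10.5 (safety analysis) or 10.7 (missing values). SAP 5.2 rules out imputation unless specified otherwise, and section 4 is where it is specified for dates.

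**The concern.** Adverse events are recorded from the screening visit (protocol 7.3.8), so the database holds both pre-dose and post-dose events, and onset date separates them. Assigning TEAE status is a date calculation, so the section 4 rule applies to any partial onset date. The rule always picks the earliest date consistent with what is known. When the known part overlaps the month or year of first dose, that earliest date is almost always before dosing.

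An event lost this way leaves the overall, severity, relationship and Grade 3 or higher tables, the serious TEAE tables (14.3.1.7 and 14.3.1.8) and Listing 16.2.7.2 (TEAEs leading to discontinuation).

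Safety is part of the primary objective. There is one arm, so no comparator carries the same error and the absolute TEAE incidence is the safety result. The loss is concentrated just after the first injection. Protocol 5.5 expects a testosterone rise in the first week, with possible worsening of bone pain, neuropathy, hematuria or urinary obstruction. The same SAP section resolves a missing causality assessment the other way, by counting the event as drug-related.

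**Working it through.** The documents state no figure on date imputation, so there is none to reproduce. The check applies the rule as written.

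**Inputs from the documents**
- Start-date defaults: SAP section 4.
- TEAE definition and scope of the tables: SAP 11.1.
- Follow-up of 168 days: SAP 3.1.

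**Assumptions, not in the documents**
- First-dose dates are uniform over a 365-day year.
- True onset is uniform over days 1 to T after first dose.
- The year of onset is known.
- The event does not later worsen.
- An imputed date equal to the dosing date counts as a TEAE, which is the lenient reading.

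**One case.** Dose on 15 March, onset recorded as March with no day. The imputed onset is 1 March, 14 days before dosing, so the event is not a TEAE.

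**Enumeration.** Take every pair of dosing date and onset day, 365 × T pairs in all. Impute the onset and count the pair as lost if the imputed date is earlier than the dosing date. Share lost = lost pairs ÷ (365 × T).

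| Onset window | Pairs | Lost, day missing | Lost, month and day missing |
|---|---|---|---|
| Days 1–7 | 2,555 | 2,135 (84%) | 2,520 (99%) |
| Days 1–28 | 10,220 | 5,013 (49%) | 9,786 (96%) |
| Days 1–84 | 30,660 | 5,020 (16%) | 27,006 (88%) |
| Days 1–168 | 61,320 | 5,020 (8%) | 46,956 (77%) |

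**Where the loss arises.** With the day missing, only onsets in the same calendar month as the first dose can be lost. Over days 1–168 there are 5,373 such pairs, and 5,020 of them (93%) are lost; the exceptions are subjects dosed on the 1st. With the month missing, only onsets in the same calendar year as the first dose can be lost. There are 47,124 such pairs, and 46,956 (99.6%) are lost; the exceptions are subjects dosed on 1 January.

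**Direction.** The start-date default can move an onset earlier but never later. It can therefore remove a true TEAE but cannot create a false one.

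**With the first-dose check described under the fix.** The same enumeration gives 0% of post-dose events dated before dosing, in both columns.

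**The case against.** The strongest reply is about size. The percentages apply only to events with a partial onset date, and early events are the least likely to have one. Adverse events are collected on Days 0, 1, 2, 3, 7, 14, 21 and 28, and the case report form asks for the onset date (protocol 9.1). A missing month for an event first reported at a dated visit is harder still to picture. Purely as an illustration, if 1% to 5% of events lacked the day, the 168-day figure of 8.2% would give 0.082 × 1% ≈ 0.08% to 0.082 × 5% ≈ 0.4% of events misclassified. This stands: the documents do not show that the overall effect is large.

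There are also safeguards. An event that worsens after dosing is recovered by the second route in the definition. Affected events stay visible, because "The listing of all AEs will be provided in Listing 16.2.7.1", and all serious events appear in Listing 16.2.7.3. Injection-site reactions have their own graded table (14.3.9). These points stand too, but they do not restore the events to the TEAE tables.

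It can be said that section 4 is generic and never mentions adverse events; time since diagnosis is another obvious use. That is true, but TEAE status needs a date comparison, nothing in SAP 11.1 overrides the general rule, and a programmer following the SAP would apply it.

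Finally, the remedy has its own error: with adverse events collected up to 28 days before dosing, some true pre-dose events with ambiguous dates will be counted as TEAEs. This also stands, but for a safety table it is the conservative direction, and the stop-date condition limits it.

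**Conclusion.** The concern holds. Followed as written, the SAP dates some post-dose events before dosing and removes them from the TEAE tables, and nothing elsewhere in either document prevents this.

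With the day missing, the loss is confined to onsets in the calendar month of first dose; with the month missing, to the same calendar year. The shares in the table depend on uniform dosing and onset dates and on no later worsening. The direction of the error does not depend on the uniform dates.

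The effect on reported incidence scales with the number of partial dates. That number is unknown and may be small. The events remain in the all-event listings, and the efficacy result is untouched. The change should be made because the error always favours the drug, is greatest in the flare period, and is cheap to remove.

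**What to change.** Add to SAP section 4, or to 11.1, a rule for adverse event start dates:

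- If the known parts of the date (month and year, or year only) match those of the first-dose date, impute the first-dose date, unless the recorded stop date shows that the event ended before dosing.
- Otherwise use the existing defaults.
- Any event that cannot be shown to precede first dose counts as a TEAE, including one imputed to the dosing day itself. This needs saying because the current definition refers to onset after administration.

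The cost is a sentence in the SAP and a line of derivation code. TEAE counts may rise slightly, and some of the added events may truly have begun before dosing. Reporting the number of adverse events with imputed start dates would let a reader judge how much the rule matters.

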4.1 Continuous endpoints

Continuous variables will be summarized and presented as number of observations, mean, standard deviation (SD), median, range, Hodges-Lehmann estimator, and 95% CI. Changes from baseline

will be tested by paired t-test or Wilcoxon signed-rank (if data violated the normal assumption, i.e. the p-value of test of normality is <0.05) test for continuous variables using a significance level of 0.05. For summaries of quantitative data, the median, minimum and maximum value will be reported exactly as the raw data are reported; measures of central tendency (means will be reported as one decimal more than the raw data and measure of variance (SD) will be reported as the two decimals more than the raw data.

4.2 Categorical endpoints

Categorical variables will be presented by frequency and percentage.

4.3 Time-to-event endpoints

The time-to-event endpoint, percentage of subjects with testosterone suppression (≤ 50 ng/dL) from Day 28 (week 4) through Day 168 ± 5 days (week 24) will be analyzed by Kaplan-Meier method. The event is defined as occurring in subjects with a testosterone level > 50 ng/dL between Day 28 (week 4) and Day 168 (week 24), and it will be presented as number of subjects with event (event number), percentage of subjects with event, suppression rate by day 168 along with 95% confidence interval, mean, median and 95% confidence interval for median. Some situations are noted for efficacy analysis by Kaplan-Meier method:

1. The subject has an event and it will be analyzed as an event on the day of first testosterone escape.
2. The subject with more than one missing testosterone value will be censored on day of last measurement.
3. Any subject having more than one missing testosterone values will be censored on the day of last measurement before the first missing testosterone measurement.
4. If subject does not have serum testosterone suppression to castrate level (i.e. serum testosterone levels > 50 ng/dL) by Day 28 (week 4), the event date will be set as Day 28 for the analysis of percentage of subjects with testosterone suppression (≤ 50 ng/dL) from Day 28 (week 4) through Day 168 (week 24).

4.4 Sample size estimation and power

Approximately 133 subjects are expected to be enrolled in this study. A sample size of 120 will achieve 85% power to detect a difference (P1-P0) of 0.0700 by using a one-sided binomial test. The

target significance level is 0.0250. This assumes that the population proportion under the null hypothesis is 0.9000 and under the alternative to be 0.97. The estimated drop-out rate is 10%, so approximately 13 subjects may drop out from the study before Day 168 (week 24).

Currently, there are totally 144 subjects enrolled in this study.

5. DATA HANDLING PROCEDURES

5.1 Coding System

All AEs will be coded according to the MedDRA dictionary, version 21.0 or higher, and be reported by System Organ Class and Preferred Term.

Concomitant medications will be coded according to the World Health Organization (WHO) Drug Dictionary.

5.2 Missing Data Handling

For missing data related to a safety or efficacy endpoints, no missing data imputation method will be performed unless otherwise specified.

6. ANALYSIS OF STUDY POPULATIONS

In this study, there will be five populations, including intention-to treat (ITT), per protocol (PP), safety, ECG, and PK/ECG populations. The ITT and PP populations will be used for the efficacy analysis. The safety population will only be used for the safety analysis. The ECG and PK/ECG populations will be used for the ECG analysis. The populations for analysis applied in this study are defined as follows:

6.1 Intent-to-treat (ITT) Population

The Intention-To-Treat (ITT) population will consist of any subject receiving at least one dose of LMIS 25 mg.

6.2 Per-protocol (PP) Population

The Per Protocol (PP) population will be composed of those subjects who received 2 doses of LMIS 25 mg without major deviations that will impact the assessment of the primary efficacy endpoint.

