4.3. Withdrawal Criteria

Discontinuation from study is defined as discontinuation of all study visits and examinations. Participants may voluntarily withdraw from the study for any reason at any time. They may be considered withdrawn if they state an intention to withdraw, or fail to return for visits, or become lost to follow up for any other reason.

Subjects will be withdrawn from the study if any of the following occurs during the study period, i.e. from screening visit to the end of study (EOS):

- (1) Lost to follow-up
- (2) Subject withdrew consent
- (3) In investigator's opinion that treatment with prohibited medications is needed
- (4) Adverse event/serious adverse event
- (5) Protocol violation (please provide specific reason)
- (6) Lack of efficacy as determined by investigator
- (7) Subjects with persistent, non-castrate serum testosterone levels (>50 ng/dL)
- (8) Other

Subjects who are withdrawn due to AEs or SAEs will be followed until these events are resolved or until the event is considered stable.

Should a subject's testosterone concentration be above the castration level (> 50 ng/mL) at or after Visit 9 (Day 28/week 4), an extra visit for confirmation of testosterone level will be issued immediately. Subjects will be withdrawn from the study at the time of confirmation from the repeat testosterone analysis. The investigators can provide other alternative treatments promptly to these withdrawn subjects in accordance with standard clinical practice.

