10.2. Analysis Population

In this study, there will be three populations, including intention-to treat (ITT), per protocol (PP), and safety populations. The ITT and PP populations will be used for the efficacy analysis. The safety population will only be used for the safety analysis. The populations for analysis applied in this study are defined as follows:

1. The Intention-To-Treat (ITT) population will consist of any subject receiving at least one dose of LMIS 25 mg.
2. The Per Protocol (PP) population will be composed of those subjects who received 2 doses of LMIS 25 mg without major deviations that will impact the assessment of the primary efficacy endpoint.
3. The safety population will consist of any subject receiving a dose of LMIS 25 mg.

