The duration of time to reach a serum testosterone of >50 ng/dL is calculated from Day 28 to Day 168 or Day of Discontinuation. The duration of time to reach a serum testosterone of >50 ng/dL will be summarized and presented as number of subjects with event (event number), percentage of subjects with event, suppression rate by day 168 along with 95% confidence interval, mean, median and 95% confidence interval for median. A positive outcome to the study will be achieved if the lower 95% confidence interval bound for the response rate at Day 168 is greater than 90%.

Subjects exhibiting post-suppression breakthrough of serum testosterone to >50 ng/dL will also be summarized based on a subset for subjects who reach castration on day 28. The calculation formula is: [The subjects exhibiting post-suppression excursions of serum testosterone to >50 ng/dL at specific visit] / [The total number of subjects who reach castration at day 28 and has nonmissing serum testosterone value at specific visit] x 100%. It will be summarized as count, percentage and exact 95% CI for binomial proportion.

The summary of primary efficacy analysis will be presented as following:

[Table 14.2.1](#): Summary of Subjects with a Serum Testosterone Concentration Suppressed to Castrate Levels (ITT Population)

[Table 14.2.2](#): Summary of Subjects with Serum Testosterone Suppression Maintained from Day 28 through Day 168 (ITT Population)

[Table 14.2.3](#): Summary of Subjects Exhibiting Post-Suppression Breakthrough of Serum Testosterone to >50 ng/dL (ITT Population)

Table 14.2.13: Summary of Subjects with a Serum Testosterone Concentration Suppressed to Castrate Levels (PP Population)

Table 14.2.14: Summary of Subjects with Serum Testosterone Suppression Maintained from Day 28 through Day 168 (PP Population)

Table 14.2.15: Summary of Subjects Exhibiting Post-Suppression Breakthrough of Serum Testosterone to >50 ng/dL (PP Population)

Also, the Kaplan-Meier curve for duration of time to reach a serum testosterone of >50 ng/dL will be presented in Figure 14.2.1 and Figure 14.2.2 for ITT and PP populations.

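### The two-dose rule removes early testosterone failures from the per-protocol set because of their outcome, and the >90% success criterion does not say whether ITT or PP decides

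*SAP*

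**What the plan says.** **Analysis sets.** ITT takes anyone given at least one dose. PP takes "those subjects who received 2 doses of LMIS 25 mg without major deviations that will impact the assessment" of the primary endpoint (SAP 6.2). Protocol 10.2 has the same rule: "subjects who received 2 doses of LMIS 25 mg without major deviations".

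**Withdrawal.** Under Protocol 4.3, a value above the castrate level from Visit 9 (Day 28) on triggers an immediate extra visit, and then: "Subjects will be withdrawn from the study at the time of confirmation from the repeat testosterone analysis". Dose 2 is given on Day 84.

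**Events.** SAP 4.3 and SAP Table 9.1-1 count a testosterone value above 50 ng/dL as an event on the day of first escape, whether or not the man discontinued. Lack of suppression by Day 28 is an event on Day 28.

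**Success.** SAP 9.1 calls the study positive "if the lower 95% confidence interval bound for the response rate at Day 168 is greater than 90" per cent. It names no population. SAP 6 says "The ITT and PP populations will be used for the efficacy analysis" and ranks neither. The Kaplan-Meier table is produced for ITT (14.2.2) and again for PP (14.2.14, "Summary of Subjects with Serum Testosterone Suppression Maintained from Day 28 through Day 168 (PP Population").

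**The concern.** Whether a man is in PP depends partly on the endpoint itself. A man who fails in the first 12 weeks, is confirmed and is withdrawn never receives dose 2, so he drops out of both the numerator and the denominator of the PP rates. A man who fails after dose 2 stays in as an event. PP therefore cannot serve as an independent check on ITT. Part of any agreement or disagreement between them comes from how the set was built.

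This would be a matter of presentation if the SAP said which result decides. It does not. If ITT missed the 90% bound and PP met it, or the reverse, the plan has no rule, and a choice made after seeing both results would not be credible.

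**Working it through.** **1. The plan's own figure.** Protocol 10.1 and SAP 4.4: n = 120, null 0.90, alternative 0.97, one-sided 0.025, power 85%. The exact binomial test allows at most 5 failures: P(X ≤ 5 | 120, 0.10) = 0.016, and P(X ≤ 6) = 0.038 is too large. Power is P(X ≤ 5 | 120, 0.03) = 84.7%. The stated figure is reproduced.

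**2. The route out of PP.**

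| Man's course | ITT | PP |
|---|---|---|
| >50 ng/dL from Day 28, confirmed and withdrawn before dose 2 | Event | Excluded (one dose) |
| >50 ng/dL before dose 2, not confirmed or confirmed only after dose 2 | Event | Event |
| >50 ng/dL after dose 2 | Event | Event |
| Suppressed, leaves before Day 84 | Censored | Excluded |
| Suppressed, major deviation affecting the primary endpoint | Kept | Excluded |

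Row 1 raises the PP rate. Rows 4 and 5 shrink PP without removing failures, which lowers its bound. The net effect can go either way.

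**3. Can failures be seen in time?** Protocol 7.2.1 samples all men on Days 28, 56 and 77 before the dosing day (Day 42 in the first 30 only). Bioanalytical samples are batched, which may delay recognition past Day 84. The same section allows faster central-laboratory tests. Early confirmation is possible; its frequency cannot be read from the documents.

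**4. Illustration.** N = 144 is the enrolment in SAP 4.4. The counts are assumptions: 9 failures, 5 of them removed before dose 2, no censoring before Day 168. The SAP names no interval method. I use the log-log bound: S = 1 − f/n, se = √[S(1 − S)/n], lower bound = S^exp{1.96·se/(S·|ln S|)}.

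- ITT: S = 135/144 = 0.9375, se = 0.0202, exponent exp(0.653) = 1.922, bound 0.9375^1.922 = 88.3%. Fails.
- PP: S = 135/139 = 0.9712, se = 0.0142, exponent exp(0.980) = 2.665, bound 92.5%. Passes.
- PP with 13 suppressed men also excluded: 122/126 = 0.9683, bound 91.8%. Passes. The 13 is borrowed from the planned drop-out in Protocol 10.1.

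| Lower bound | ITT 9/144 | PP 4/139 | PP 4/126 |
|---|---|---|---|
| Log-log | 88.3% | 92.5% | 91.8% |
| Linear | 89.8% | 94.3% | 93.8% |
| Exact | 88.5% | 92.8% | 92.1% |

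The reversal holds with all three methods. The number of early removals needed does not: with 13 excluded and only 3 of the 9 failures removed (6 events in 128), the bound is 89.9% log-log, 90.1% exact and 91.7% linear.

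**5. How likely is a conflict?** Let failures be Binomial(144, 1 − true rate). Each is removed early independently with the stated share. Then 13 suppressed men leave PP, and the log-log bound is recomputed. ITT passes with at most 7 failures (bound 90.07%).

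| True rate | Early share | ITT passes | PP passes | ITT fails, PP passes | ITT passes, PP fails |
|---|---|---|---|---|---|
| 97% | 10% | 93.1% | 89.7% | 0.2% | 3.5% |
| 97% | 25% | 93.1% | 93.7% | 1.6% | 1.0% |
| 97% | 50% | 93.1% | 98.4% | 5.4% | 0.1% |
| 90% | 10% | 2.0% | 1.6% | 0.1% | 0.6% |
| 90% | 25% | 2.0% | 4.2% | 2.3% | 0.2% |
| 90% | 50% | 2.0% | 26.9% | 24.9% | <0.1% |

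With no suppressed man excluded, the PP pass chance at a true rate of 90% is 3.6%, 8.7% or 41.6% for the three shares.

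**The case against.** Four points deserve weight.

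- **The sponsor's earlier study shows no gap.** Protocol 1.3 reports 97.0% in both ITT (137) and PP (124) for the 50 mg product, with four failures, two of them on Day 28. Ignoring censoring, dropping those two from PP would give 122/124 = 98.4%; keeping all four gives 120/124 = 96.8%. The reported figure is closer to the second, which suggests that early failures mostly stayed in. That study's PP and withdrawal rules are not set out in full, so this supports a small effect and does not rule one out.
- **The illustration is chosen to flip.** At 97%, about 4 failures are expected in 144 (0.03 × 144 = 4.3). Taking 13 suppressed men out of PP is also rough, because a man who leaves after dose 2 can remain in. With 5 of 9 failures removed, the log-log reversal disappears once 36 suppressed men are excluded (4 events in 103, bound 89.98%).
- **Requiring the full regimen is a conventional PP choice.** I accept this. The problem is only the men who miss dose 2 because they failed.
- **Part of the record is unreadable.** The synopsis tick-boxes for the efficacy population were lost in the text. The legible text there lists both sets and ranks neither.

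A reader might infer that the primary result is biased, or that the false-success rate is 41.6%. The documents support neither. ITT keeps every escape as an event. The 41.6% arises only if PP decides, the true rate is 90%, half of the failures leave early and nobody else is excluded. Nor does PP always favour the product: at a 10% early share with 13 men excluded, it is harder to pass than ITT.

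**Conclusion.** The point stands and should be fixed. As written, PP drops failures that are confirmed and withdrawn before dose 2, which biases the PP Day 28 and Kaplan-Meier rates upward by this route, and no text says which set the >90% criterion uses. The size is unknown and probably small. It depends on the early share, on other PP exclusions and on the interval method, none of which the documents give. Under the assumptions shown, a conflict in PP's favour at the design rate of 97% has a chance between 0.2% and 5.4%. The missing decision rule matters more than the expected size of the bias.

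A separate minor point: Protocol 4.3 gives the withdrawal threshold in two units, "Subjects with persistent, non-castrate serum testosterone levels (>50 ng/dL" in item 7 and "testosterone concentration be above the castration level (> 50 ng/mL) at or after Visit 9 (Day 28/week 4" in the paragraph after the list. They differ by a factor of 100. Because withdrawal affects who can enter PP, the passages must be reconciled.

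**What to change.** 1. **SAP 9.1:** state that the >90% criterion is judged on the ITT Kaplan-Meier estimate at Day 168, and that PP is supportive.
2. **SAP 6.2:** keep the two-dose requirement with one exception. Men with testosterone above 50 ng/dL (the SAP's event definition) at or after Day 28 and before dose 2, who did not receive dose 2, stay in PP as events if they have no other major deviation. Suppressed men who miss dose 2 remain excluded, as now.
3. **Protocol 4.3:** reconcile the two units.

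In the illustration, change 2 puts the 5 early failures back. PP is then 135/144 with a bound of 88.3%, equal to ITT, or 122/131 = 93.1% with a bound of 87.2% if 13 suppressed men are excluded. Both sets then fail.

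**Cost.** Two sentences in the SAP, which by its section 1 takes precedence over the protocol, plus a protocol correction for the units. Neither SAP change touches dosing or withdrawal. The PP rate may be slightly less favourable. Because the trial is open-label and 144 men are already enrolled, the SAP wording should be fixed and dated before the primary results are tabulated.
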